To attempt to reduce these delays in urgent and emergency care, Spectra Analytics developed an Al Triage add-on system for the standard PATCHS product (called 'PATCHS Al Triage' for this document) in project IRAS ID: 264891. PATCHS Al Triage uses natural language processing (NLP) and deep learning to analyse online consultations to predict whether they are either urgent, emergency, or routine based on the above definitions.

PATCHS AI Triage was initially developed in 2020 using 43,998 online consultations for 37,000 patients to 52 GP practices using PATCHS. The unstructured free-text written by patients in their online consultation, type of online consultation submitted (e.g. new health problem, administrative query), and patient demographics were used as inputs to the model. The manually applied 'urgent' and 'emergency' flags from GP practice staff were used as model outputs. Data were split into training (90%) and test (10%) datasets. AI model training was optimised for a high true positive rate based on findings from co-design workshops where GP practice staff and patients felt it was most important that AI Triage systems missed as few urgent or emergency online consultations as possible. The true positive rate of PATCHS AI Triage to detect urgent and emergency online consultations was 86% in the training dataset and 84% in the test dataset. Subsequently in 2021, PATCHS AI Triage was evaluated in 14 early adopter GP practices covering inner city and urban areas in the north and south of England. Using triage decisions made by GP practice

staff to define urgent and emergency online consultations, its true positive rate was 94% in 19,805 online consultations previously unseen by the AI prospectively for 9,725 patients (21% non-white). Qualitative research with 20 staff at early adopter practices showed they found PATCHS AI Triage both acceptable and useful. Work is currently underway to re-train PATCHS AI Triage to ensure its performance has been maintained over time, and scientific publications reporting its development and validation are being prepared for peer-review.

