If a patient opts out of sharing their anonymised data for research purposes with UoM (Appendix 1, Screenshot 6), we will withdraw their data. When a patient has used PATCHS it is impractical to find out whether they subsequently lose capacity as all registered patients at the GP practices can use PATCHS. If a GP practice staff member uses PATCHS then subsequently loses capacity, we will continue to use the data they provided before losing capacity. If data have already been extracted, we will be unable to withdraw participants' data because the data will have been anonymised and we will be unable to identify the participant.

9) OUTCOME MEASURES

Primary outcome measure

Our primary outcome measure is the proportion of delays in completing urgent and emergency online consultations at the patient-level:

(delayed urgent online consultations + delayed emergency online consultations)

- ÷ (total urgent patient online consultations
- + total emergency online consultations)

It was chosen because patients and clinicians we consulted during our PPI work felt it was the most clinically important outcome measure. Delays will be measured by the difference between the date-time that an urgent or emergency online consultation was submitted by a patient in PATCHS and the date-time the consultation was completed in PATCHS by GP practice staff. Based on our PPI work, we will consider an urgent online consultation delayed if it is not completed within 48 hours and an emergency online consultation delayed if it is not completed within 24 hours. Online consultations that have not yet been completed but were submitted by patients more than 48 hours previously at the point of data extraction will be included. In intervention practices we define online consultations as urgent or emergency where a GP practice staff member has applied a triage decision as either 'urgent' or 'emergency', or where AI Triage predicts an online consultation as 'urgent' or 'emergency' which is unchanged by staff. We will assume that patients who receive a signpost message and cancel their online consultation will have sought care from other services and not experienced a care delay. In control practices we define online consultations as urgent and emergency only if GP practice staff apply a triage decision as either 'urgent' or 'emergency'.

Secondary outcome measures

Interrupted Time Series Analysis

Patient-level - binary

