To analyse continuous patient-level outcome measures (absolute time to completion or staff user action for urgent and emergency online consultations – combined and separate; absolute time to completion or staff user action for routine online consultations) we will use mixed-effects linear regression models with all other aspects of the analysis remaining the same.

If multiple online consultations are submitted by the same patient, we will randomly sample one per patient for analysis. Multiple online consultations from the same patient are expected to be infrequent, though if this approach adversely affects reaching our sample size target we will instead include all online consultations with a patient-level variable in our models.

To analyse count GP practice-level outcome measures (proportion of total appointments provided by GP practices; proportion of online consultations submitted by patients; proportion of patients with emergency department attendances; proportion of online consultations with emergency department attendances; proportion of patients with emergency hospital admissions; proportion of online consultations with emergency hospital admissions) we will use negative binomial regression models with appropriate offset terms for the denominators. For example, GP practice population size (40) or number of whole-time equivalent GPs per 1000 patients (39).

[figure not shown]

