Similar to the interrupted time series analysis, limitations with the above approach include that: staff triage decisions could be applied by non-clinicians; the true urgency of an online consultation may only be apparent when further information has been obtained from the patient (e.g. over the telephone); we assume AI Triage predictions for patients who receive a signpost message and cancel their online consultation is correct. We will therefore conduct sensitivity analyses where: we restrict triage decisions to those only made by clinicians; the final triage decision when the online consultation is resolved is used; patients who receive a signpost message and cancel their online consultation are excluded. As mentioned above, multiple online consultations from the same patient are expected to be infrequent, though will be assessed by using a patient-level variable in models and by re-running analyses after randomly sampling one online consultation per patient.

Health inequalities

We will assess the potential influence of AI Triage on health inequalities across different age groups, sexes, ethnic backgrounds, Index of Multiple Deprivation quintiles, and non-English language usage. In dose and reach metrics we will compare the proportion of each sub-group in the population using online consultations in intervention and control practices in the pre- and intervention periods (44), and to the characteristics of the wider practice populations in National General Practice Profiles (38).

Each accuracy metric will be tested for differences in performance between patient sub-groups. We will also undertake a failure case analysis to explore factors why AI Triage may have predicted incorrectly (46)

by comparing the characteristics of patients who have submitted online consultations classified as false positive and negatives to those of true positive and negative predictions ('error auditing') (47). Additional factors to test will include those related to the online consultation (including type of online consultation, time and day of submission), GP practice staff who applied the triage decision (including role, experience using PATCHS), and GP practice (including size, geographic location, experience using PATCHS).

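### One random consultation per patient departs from section 9's consultation denominators, and its justification, that repeats are rare, conflicts with the protocol's own counts for all-consultation outcomes

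*Protocol*

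**What the plan says.** Protocol section 9 defines the primary outcome as a ratio of consultation counts. Its numerator is "delayed urgent online consultations + delayed emergency online consultations" and its denominator is all urgent and emergency consultations. The other binary patient-level outcomes (cancelled, assigned to clinicians) also have consultations as denominators. Section 9 and research question 1 nevertheless label the primary outcome as patient-level.

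Section 11.1 (Modelling) then sets the rule for repeats: "If multiple online consultations are submitted by the same patient, we will randomly sample one per patient for analysis". The reason is "Multiple online consultations from the same patient are expected to be infrequent". There is a fallback: "if this approach adversely affects reaching our sample size target we will instead include all online consultations", with a patient-level variable that is not described further.

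Section 5 gives two counts of forms and patients: "43,998 online consultations for 37,000 patients" in the development data, and 19,805 consultations "prospectively for 9,725 patients" in the early-adopter evaluation.

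For the process evaluation, section 11.1 treats repeats in both ways: "using a patient-level variable in models and by re-running analyses after randomly sampling one online consultation per patient". The sensitivity analyses listed for the interrupted time series contain no such comparison.

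**The concern.** Sampling one form per patient gives every patient equal weight, whereas the ratios in section 9 give every consultation equal weight. The two agree only if delay, and the effect on delay, are unrelated to how many forms a patient sends. The protocol gives no ground for assuming that.

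The sampling also discards data already held, on a premise that section 5 does not bear out for outcomes counted over all consultations.

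The sampling frame is open too. The main parameter is the interaction of group and period. If the draw is one per patient over the whole study, whether a pre-intervention form is kept depends on how many forms the patient sends later. AI Triage may change that number in one arm. Finally, which weighting is used depends on whether a sample-size target is met.

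**Working it through.** **1. Plan's own figure.** For 25% versus 20%, 90% power and 5% alpha (two-sided assumed), with pooled variance:
n = [1.960·√(2·0.225·0.775) + 1.282·√(0.25·0.75 + 0.20·0.80)]² / 0.05² = 1,464 per group, or 2,928 in total. This matches section 11.2. The target counts urgent and emergency consultations.

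**2. Rows dropped, all consultations (section 5).** Share dropped = 1 − patients/consultations.
- Development: 43,998/37,000 = 1.19 per patient; 1 − 37,000/43,998 = 15.9%.
- Early adopters: 19,805/9,725 = 2.04 per patient; 1 − 9,725/19,805 = 50.9%.

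These shares apply to cancellation and assignment to clinicians. A similar share may be lost for routine completion and action times, since most forms are routine.

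**3. Rows dropped, primary outcome.** Section 5 puts urgent and emergency forms at 6.5% and gives no repeat rate for them, so the following is modelled. Assume zero-truncated Poisson form counts, with the draw made within urgent and emergency forms. Share dropped = 1 − (1 − e^(−μ))/μ, where μ = 0.065·λ.
- 1.19 per patient (λ = 0.357): about 1%.
- 2.04 per patient (λ = 1.642): about 5%.
- 4 per patient (assumed, for a longer window): about 12%.

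If urgency clusters within patients (gamma shape 1 to 0.1, assumed), the loss is about 10% to 34% at 2.04 per patient and 20% to 53% at 4. If the draw comes before the restriction, and urgency is unrelated to form count, the 16% to 51% of step 2 applies instead.

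**4. Power for the primary outcome.** Approximation with 20 practices per arm and m forms per practice:
d = ln(0.25/0.75) − ln(0.20/0.80) = 0.288; variance = 2τ²/20 + 1/(20·m·0.1875) + 1/(20·m·0.16); power = Φ(d/√variance − 1.96).

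| τ² | m = 600 (all kept) | m = 295 (49.1% kept) | Table 1 (95% CI) |
|---|---|---|---|
| 0.1 | 78% | 75% | 72% (62.1–80.5) |
| 0.2 | 51% | 49% | 53% (42.8–63.1) |
| 0.825 | 17% | 17% | 21% (13.5–30.3) |

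The full-data values lie inside the plan's simulation intervals. Practice variance dominates, so even halving the rows costs three points at most.

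**5. Weighting (assumed figures).** Suppose 80% of patients send one form (23% delayed) and 20% send three (33% delayed).
- By consultation: (0.8·0.23 + 0.6·0.33)/1.4 = 27.3%.
- By patient: 0.8·0.23 + 0.2·0.33 = 25.0%.

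This is a difference in level within one group, not in the interaction. It is zero if form count is unrelated to delay.

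**6. Retention under an overall draw.** A patient with a forms before and b forms after the index date keeps any given form with probability 1/(a + b). With a = 1, the pre-intervention form is kept with probability 1, 1/2 or 1/3 for b = 0, 1 or 2.

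**7. The switch.** Planned forms in the intervention period: 40 × 50 × 12 = 24,000. Losing 15.9% leaves 20,184 and losing 50.9% leaves 11,784. To fall below 2,928 the loss must exceed 1 − 2,928/24,000 = 87.8%. With only 3 practices per arm, 6 × 50 × 12 = 3,600 would fall to about 3,028 or 1,768.

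**The case against.** The strongest reply is that the harms are small for the outcome that matters most. The figure of 2.04 counts all forms. The remark about infrequent repeats sits beside a target that counts urgent and emergency forms, and nothing in the protocol contradicts it for those. One of the two ratios in section 5 is only 1.19. This stands: the conflict is shown for the all-consultation outcomes only.

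A reader might infer several stronger points that the protocol does not support:
- **That half the primary data are lost.** No repeat rate is given for those forms, and the power cost is small in any case. A widening of intervals by √2.04 = 1.43 would require independent rows and no practice variance, so it is a ceiling.
- **That the primary estimand is plainly changed.** The patient-level label cuts both ways, and the illustration in step 5 is assumed. If the mix of patients and its relation to delay are the same in both arms and periods, much of the gap would cancel in the interaction.
- **That a 24-month draw biases the comparison.** An overall draw is one reading of an unstated frame, and the size of any bias is unknown. A separate analysis plan may settle the frame.
- **That the switch invites effect-driven choice.** Its trigger is a count. The analysts are blinded to which group is which (section 8.4), and time-series data are transferred only after the intervention period (section 10).

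The different order used in the process evaluation is not a contradiction, because it is another analysis. It does show that the team already has the better pattern in hand.

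**Conclusion.** The point holds as a mismatch between outcome definition and analysis rule that is cheap to repair, not as a threat to the primary result.

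Section 9 counts consultations; section 11.1 analyses one per patient. For cancellation and assignment to clinicians, about 16% to 51% of rows would be dropped, provided the study practices resemble one of the two datasets in section 5. For the primary outcome the loss is unknown. It is probably well below half if the draw is made within urgent and emergency forms, unless urgency clusters strongly within patients, and its effect on power is minor.

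The order and period of the draw need to be fixed. Under an overall draw, retention of baseline forms would depend on behaviour after allocation. The fallback moves the weighting from patients to consultations, but with 20 practices per arm it would almost never be used. It becomes relevant only if recruitment falls far short, a risk the protocol itself discusses.

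**What to change.** In section 11.1:
- Make the analysis of all consultations primary for every patient-level outcome, with the practice random effect and standard errors clustered by practice. Clustering by practice also covers repeat forms from one patient. A patient random effect is optional; it may be weakly identified for the primary outcome if most patients contribute a single urgent or emergency form.
- Run one-per-patient sampling as a sensitivity analysis, drawn within each outcome's own denominator and separately within each period.
- Delete the switch tied to the sample-size target.

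This matches the denominators in section 9, uses data already held, and is close to the plan's own fallback and its process-evaluation approach. The cost is a change of wording and slightly more modelling work. Confidence intervals would rest on about 40 clusters, which should be acknowledged when they are reported.

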Control GP practices will continue to use PATCHS without AI Triage as described above and will manually triage patient forms. By default, patient forms are ordered in the inbox by date-time ascending i.e. with the oldest patient forms at the top of the inbox and the newest ones at the bottom. Patient forms are manually triaged by GP practice staff using the categories above, which changes their order in the inbox to aid prioritisation (Appendix 1, Screenshot 2):

- Emergency: adds a red flag icon to the message and sorts it to the top of the PATCHS inbox.
- Urgent: adds an orange flag icon to the message and sorts it to the top of the PATCHS inbox below 'Emergency' forms.
- **Routine**: neither urgent nor emergency. Grey or purple flag icons are added and the position of the message in the PATCHS inbox does not change.

Patients do not receive any additional messages if they submit an urgent or emergency form.

Intervention GP practices: PATCHS with AI Triage (automated triage)

Intervention GP practices will use PATCHS as described above with assistance from the latest version of AI Triage as an add-on feature (called Urgency and Signpost AI in the PATCHS help documentation (27)(28); currently model version 368d85c790a743928be3dd711f914fcc). AI Triage uses the unstructured free-text written by patients in their online consultation, type of online consultation submitted (e.g. new health problem, administrative query), and patient demographics (age and sex) to predict online consultations as either 'emergency', 'urgent', or 'routine'. AI Triage communicates its predictions with GP practice staff and patients in the following ways:

- **GP practice staff**: The manual triage process described above for control GP practices is automated i.e. when patients submit a form that is predicted as emergency or urgent by Al Triage, a red or orange flag icon is automatically added respectively, and the forms are sorted to the top of the PATCHS inbox (Appendix 1, Screenshot 2). The triage decisions (Appendix 1, Screenshot 1) are pre-populated for GP practice staff, which they can change if they disagree (e.g. upgrade or downgrade the urgency).

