- Patients: If patients submit an online consultation predicted by AI Triage as emergency at any time or urgent when their GP practice is closed, they immediately receive an automated 'signposting' message advising them to contact emergency services or the NHS 111 'out of hours' service, respectively (Appendix 1, Screenshot 3). They will also be presented with supporting advice from NHS.uk if relevant articles exist on the website. If their online consultation is predicted as 'routine', the patient may be presented with self-help advice from NHS.uk if relevant articles exist on the website (Appendix 1, Screenshot 4). Patients can accept this advice and cancel their online consultation, and the GP practice will not receive the form in their PATCHS inbox but can view it in a

Version 1.1 01/03/2024 IRAS ID: 331286

separate 'cancelled' folder if they wish. Alternatively, patients can ignore the advice and continue to submit their online consultation to their GP practice at their own risk.

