GP practices will be randomly allocated to intervention (AI Triage now) or control (AI Triage later) groups in blocks of 5 practices in each arm (control and intervention) using the *runiform* command in Stata 18 with a target of 20 in each group. Depending on the response rate we may increase or decrease block size, and through a combination of randomisation and algorithmic approaches (31) using appropriate statistical software (32) we will attempt to match the two groups as closely as possible on patient population size (40), Index of Multiple Deprivation (34), monthly volume of online consultations per 1000 patients, baseline levels of the primary outcome measure, and baseline prevalence of urgent and emergency online consultations. We will also explore the possibility of matching GP practices on geographic region, rurality (36), number of whole-time equivalent GPs per 1000 patients (39), mix of patient ethnicities, and levels of patient morbidity (40), though given the target sample size is relatively small this may not be possible. Where we cannot match characteristics, we will attempt to adjust for them in our statistical models.

This is a single-blind study. The UoM research team will not know which GP practices are allocated to intervention or control groups. Due to the nature of the intervention GP practices cannot be blinded. The

UoM research team will randomly allocate GP practices to "0" or "1" groups using the approach described above. The allocation sequence will be provided to Spectra Analytics who will use statistical software to randomly allocate "0" or "1" to be the intervention group. They will then approach GP practices in the intervention group to offer them AI Triage as described elsewhere. Spectra Analytics will retain the mapping key and not share it with the UoM research team until after data analysis is finalised. The interrupted time series analysis (including analysis of the primary outcome measure) will not be undertaken until the end of the intervention period. Analyses will be undertaken by the UoM research team only not Spectra Analytics.

8.5 Participants who withdraw consent or lose capacity to consent:

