Limitations with the above approach include that: staff triage decisions could be applied by non-clinicians which could be systematically different to those applied by clinicians (43); we assume that patients who receive a signpost message and cancel their online consultation have not experienced a care delay; and the triage decisions made by GP practice staff may be highly variable. We will therefore conduct sensitivity analyses where: we restrict triage decisions to those only made by clinicians; we exclude patients who receive a signpost message and cancel their online consultation; we define online consultations as urgent and emergency in intervention and control practices if they are predicted as either 'urgent' or 'emergency' by Al Triage. We will also conduct sensitivity analyses where we sub-sample practices and patients with similar: baseline levels of the outcome measure, monthly volume of online consultations per 1000 patients, prevalence of urgent and emergency online consultations, agreement with AI Triage predictions, contributions to AI Triage model training, and other variables matched during randomisation and model adjustment where appropriate. Further sensitivity analyses may be undertaken based on findings from the process evaluation (44), for example, we may find a cohort of practices that did not engage with the Al Triage training, and we may test the hypothesis that Al Triage was less effective at reducing delays in urgent and emergency online consultations for them. We will also explore using an alternative analysis approach, interacting practice group with time and period to estimate the adjusted intervention time series. For example, a difference-in-difference method pooling the outcome (and the offset) in the preand intervention periods.

Health inequalities

We will use the pre-intervention period to assess for inequalities in the influence of patient characteristics on experiencing urgent and emergency care delays in both the pre- and intervention periods. We will use

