 using PATCHS altogether: We will include them in the main analysis in the intervention group. We
 will undertake sensitivity analyses where we use their data as intervention GP practices up to the
 point they cross over and where we exclude them entirely from the analysis.

11.2 Sample Size:

Our sample size calculation is based on our primary outcome measure. Patients and clinicians we consulted during our PPI work felt an absolute reduction of 5% in the proportion of urgent and emergency online consultation delays would be meaningful. Assuming a baseline delay of 25% from our prior research and a simple before-after design, we estimate a minimum of 2928 urgent and emergency (combined) online consultations across both intervention and control GP practices during the intervention period are required to detect a minimum absolute reduction of 5% to 20% with 90% power and 5% alpha. Further assuming 50 urgent and emergency online consultations (combined) on average for a GP practice per month and a 12-month intervention period, this translates to a minimum of three intervention and three control practices. However, this does not account for between-practice variability. Consequently, we will aim to recruit 20 intervention and 20 control practices. Between-practice variability can be difficult to

predict, so we have estimated the power of this sample size for different assumptions of between-practice variance using ipdpower for Stata (48), which calculates power for mixed-effects models using simulations (Table 1). To minimise between-practice variance in our sample, we will recruit intervention and control GP practices in blocks (described in section 8.4). If we find that between-practice variance is high, we will target recruitment of practices with similar baseline characteristics for the outcome measure in subsequent stages.

Table 1: Study power simulations

Between-practice variance	Power (%)	95% confidence interval (%)
0	100	96.4-100.0
0.1	72	62.1-80.5
0.2	53	42.8-63.1
0.825	21	13.5-30.3

12) DATA AND INTERVENTION ACCESS POST-STUDY

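### The only re-analysis of the 'signposted and cancelled means no delay' assumption is exclusion, which leaves untested the case where cancelled forms are later than the rest

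*Protocol*

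**What the plan says.** Section 9 of the protocol sets the primary rule: "We will assume that patients who receive a signpost message and cancel their online consultation will have sought care from other services" and had no care delay. Such a form therefore adds to the denominator of the delay proportion and never to the numerator.

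Section 7.2 says who is affected. With AI Triage, a patient is signposted when the form is predicted "as emergency at any time or urgent when their GP practice is closed". A patient who accepts the advice can cancel, and the form then stays out of the practice inbox. Without AI Triage, "Patients do not receive any additional messages if they submit an urgent or emergency form".

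Under Sensitivity analyses for the interrupted time series, section 11.1 lists the no-delay assumption as a limitation and answers it with one re-analysis: "we exclude patients who receive a signpost message and cancel their online consultation". The process evaluation repeats the exclusion for its own measures. The parameter of interest is the interaction of practice group with study period.

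**The concern.** A sensitivity analysis of an untestable assumption should show how the result moves as the assumption is varied in the unfavourable direction. Here the assumption is that the delay risk of cancelled forms is zero. The unfavourable direction is that some of these patients accepted the advice, cancelled and were not seen in time elsewhere. PATCHS cannot show this, because a cancelled form has no staff completion time.

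Exclusion goes only part of the way. It gives the same AI-cell proportion as assuming that cancelled forms carry the average risk of the forms that stayed. The selection rule gives some reason to expect more than that. Emergencies have the shorter limit (24 hours against 48), and for closed-hours urgent forms the clock runs from submission with no stated pause. If cancelled forms are later than the rest, both planned runs err in favour of AI Triage and the reader has no third run to show it.

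**Working it through.** **The plan's own figure.** Section 11.2 gives the inputs: "Assuming a baseline delay of 25% from our prior research and a simple before-after design", to "detect a minimum absolute reduction of 5% to 20% with 90% power and 5% alpha". For two proportions with pooled variance, two-sided 5% and no continuity correction:

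n per group = [1.960·√(2·0.225·0.775) + 1.282·√(0.25·0.75 + 0.20·0.80)]² / 0.05² = 1464.

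With equal groups the total is 2928, which matches the protocol exactly. So 25% is the baseline and 5 points is the yardstick below.

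**Notation for the AI cell (AI practices, intervention period).**
- c: share of urgent/emergency forms signposted and cancelled. Not in the protocol; assumed 5–20%.
- p: delay risk of the forms that were not cancelled.
- q: risk that the patient behind a cancelled form had a care delay. Not in the protocol and not observable in PATCHS; assumed.

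**What each run estimates.**
- Primary rule: (1−c)p, which sets q = 0.
- Exclusion: p, which sets q = p.
- All cancelled forms late (not planned): (1−c)p + c, which sets q = 1.
- True AI-cell risk: (1−c)p + cq.

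The error of the primary rule is −cq. The error of exclusion is p − [(1−c)p + cq] = −c(q−p). Exclusion favours AI Triage if q > p, is unbiased if q = p, and works against AI Triage if q < p.

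**No true effect.** Hold the true AI-cell risk and the other three cells at 25%, so p = (0.25 − cq)/(1−c). Apparent effects in percentage points:

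| c | q | p | Primary | Exclusion |
|---|---|---|---|---|
| 5% | 10% | 25.8% | −0.5 | +0.8 |
| 5% | 25% | 25.0% | −1.25 | 0 |
| 5% | 50% | 23.7% | −2.5 | −1.3 |
| 10% | 10% | 26.7% | −1.0 | +1.7 |
| 10% | 25% | 25.0% | −2.5 | 0 |
| 10% | 50% | 22.2% | −5.0 | −2.8 |
| 20% | 10% | 28.75% | −2.0 | +3.75 |
| 20% | 25% | 25.0% | −5.0 | 0 |
| 20% | 50% | 18.75% | −10.0 | −6.25 |

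**Is q > p plausible?** An illustrative simulation assumed opening Monday to Friday 08:00–18:30, exponential working time to completion, no priority for emergencies, 20–50% of forms sent when closed and 10–30% emergencies, calibrated to 25% late overall. Late forms were 15–21% (urgent, open), 24–31% (urgent, closed), 27–37% (emergency, open) and 49–56% (emergency, closed). All signpost-eligible forms together were 31–34% late. Taking that range as q with c = 10%: p = (0.25 − 0.031)/0.9 = 24.3% to (0.25 − 0.034)/0.9 = 24.0%. The primary error is then −3.1 to −3.4 points and the exclusion error −0.7 to −1.0.

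**Tipping point.** Suppose the non-cancelled forms show p = 20% and the other three cells 25%. The effect vanishes when (1−c)p + cq = 25%, so q* = (0.25 − 0.20(1−c))/c.

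| c | Primary | Exclusion | All late | q* |
|---|---|---|---|---|
| 5% | 19% | 20% | 24% | 120%, so never |
| 10% | 18% | 20% | 28% | 70% |
| 20% | 16% | 20% | 36% | 45% |

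The planned runs give the first two result columns only. They say nothing about q*.

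**The case against.** The strongest reply is that exclusion is already the cautious run. For any c and p above zero, p exceeds (1−c)p, so exclusion always looks less favourable to AI Triage than the primary rule, and a large cancellation effect would appear as a gap between them. This stands, but the less favourable of two runs is not a bound.

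A reader might go further and infer that exclusion is biased towards AI Triage because it strips out the closed-hours forms most likely to be late. The documents do not support that:
- The direction depends on q against p, and the protocol gives no cancellation share and no delay rate by hour of submission.
- The removed set also contains predicted emergencies sent while the practice is open.
- The removed forms need not have counterparts in the other cells. A cancelled form counts on the AI prediction alone, whereas without AI Triage staff must apply the urgent or emergency decision. Some cancelled forms may be ones staff would have called routine, and removing those improves comparability.
- No rule in the protocol says that agreement between the two runs will be reported as robustness.

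It can also be said that the matter is covered elsewhere or belongs in the SAP. Cancellations, emergency attendances and admissions are outcomes, the process evaluation maps what follows a signpost, and further sensitivity analyses are allowed. None of these re-estimates the primary effect with cancelled forms counted as late. The run that defines urgency by AI prediction in both groups does not say that it drops the no-delay assumption. The point is also not one of silence: the protocol names the limitation and fixes a specific remedy, which does not bound it.

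**Conclusion.** The point holds in this limited form: the planned runs cover q from 0 to p and leave q > p untested, for an assumption that the protocol itself lists as a limitation and that acts on one cell of the interaction. This follows from the definitions and needs no outside figure.

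The size does rest on assumed inputs. With no true effect and 10% cancelled, exclusion is off by −2.8 points at q = 50%, by −0.7 to −1.0 at q = 31–34%, by nothing at q = 25% and by +1.7 at q = 10%. The 31–34% comes from a simulation that ignores priority for emergencies, so it illustrates plausibility and is not an estimate. A bias in favour of AI Triage is therefore possible but not established. If few forms are cancelled the issue is minor: at 5% cancelled, with 20% against 25% otherwise, no value of q removes the effect. The addition is worth making because the cancellation share is not yet known.

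**What to change.** In the section 11.1 sensitivity list, keep the exclusion run and add a tipping-point analysis. Vary the share of signposted and cancelled urgent/emergency forms counted as delayed from 0 to 100%, refit the primary model at each step, and report the share at which the primary effect disappears next to the observed cancellation share. Show the all-delayed case as the outer bound only. Do not make robustness conditional on it: that case also acts on the AI cell alone and would count as late some forms that staff might have called routine.

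The section 10 extract already holds the signposting messages and the cancellation flag, so no new data are needed. The cost is one more set of model runs and a reported range that is wider and less favourable to AI Triage.
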